#### **Incentives**

Regardless of the return of a swab, all participants will receive a nominal incentive (\$35) for completion of the Post-Swab 1 CASI and \$45 for the Post Swab 2 CASI after the second swabbing. The HRA incentive of \$50 includes completion of the Post-HRA CASI.

#### HRA

All persons will receive HRA at the Anal Dysplasia Program of the Medical College of Wisconsin by a highly trained and experienced high-resolution anoscopist. A DARE will be done on all participants. For DARE and HRA, all findings will be recorded systematically. All suspicious lesions will be documented and biopsied. If no lesions are seen on HRA, then two biopsies will be taken from two different quadrants of the anal canal to support confirmation of the anoscopists' negative finding for lesions. A senior high-resolution anoscopist will observe the HRA and HRA-directed biopsies of the HRA clinician for 5 persons. We will also monitor HSIL rates, investigate unexpected variation in HSIL rates, and assesses need for further training and observations. Importantly, the primary outcomes for all 3 aims do not rely on HRA results. The clinician will also treat external anal disease or refer for treatment, triage internal anal disease if necessary, and ask to be notified if a participant has any anus-related concerns in the following week.

A blood draw will be done during the HRA visit. The blood specimen will allow testing for factors in serum, that may be associated with anal precancers.

For DARE and HRA follow up, persons will receive usual care. HBM constructs will then be used in a brief CASI focusing on the acceptability of HRA.

After the study is finished, we will telephone participants once a year for two years and ask about screening for anal cancer that the person may have done on their own and the results of that screening.

# Medical Records

All participants will have their medical record reviewed for HPV-associated procedures or conditions. From the medical records of persons with HIV, we will abstract viral load and CD4 count information. Findings will be systematically recorded using a standardized data extraction form. All persons who are not verified as HIV-positive through medical records will receive an HIV test at the baseline clinic visit and one year later at HRA. Standard clinical practices will be followed for providing HIV test results and any needed subsequent care.

#### Results Given to Participants

Given that the HRA will identify any occult disease in the participant, the genotyping and methylation results will not be given to participants with the following exception: participants with persistent high-risk HPV will be notified by either study staff or the clinician and counseled to adhere to regular contact with a knowledgeable physician to assess future anal cancer risk. HPV genotyping and methylation status are not currently used to drive clinical decisions for anal health care. At study start, all persons will receive a DARE to rule out palpable masses or other symptoms that may indicate malignancy; however, the DARE will be delayed for 2-4 weeks after study start for persons in the home-based arm so that the proportion of persons compliant with home-based swab 1 specimen collection are not biased by the DARE.

#### **BURDEN OF TIME ON PARTICIPANTS**

#### Both arms:

Eligibility CASI– 5 minutes
Consenting – 30 minutes
Baseline CASI – 15 minutes
Travel to clinic for HRA and DARE – varies by mode of transportation
HRA and DARE – 15 minutes
HRA CASI – 5 minutes

#### Arm 1:

Home-based swab 1 - 10 minutes

Home-based swab 1 CASI – 10 minutes

Travel to clinic at baseline for DARE and anal swabbing – varies by mode of transportation

DARE and anal swabbing – 10 minutes

DARE satisfaction survey – 5 minutes

Home-based swab 2 - 10 minutes

Home-based swab 2 CASI – 10 minutes

#### Arm 2:

Travel to clinic for swab 1 and DARE – varies by mode of transportation

Clinic-based swab 1 and DARE – 10 minutes

Clinic-based swab 1 CASI – 10 minutes

Travel to clinic for swab 2 – varies by mode of transportation

Clinic-based swab 2 - 10 minutes

Clinic-based swab 2 CASI – 10 minutes

#### LABORATORY ASSAYS

#### **HPV** Genotyping

All Aim 1 specimens will be batch sent to Moffitt Cancer Center for processing (81 specimens at a time will be sent which is equal to one box and one LiPA25 run). DNA will be extracted from all specimens using the robotic MDx Media Kit (Qiagen), according to the manufacturer's instructions. The HPV SPF10 PCR-DEIA-LiPA line probe assay system will be utilized to detect 25 HPV genotypes by reverse hybridization technology. We will add control DNA from cervical cell lines with high (CaSki) and low (SiHa) HPV-16 copy numbers as well as lines that are HPV-negative (C33A) and will perform PCR to detect the presence of human beta-globin.

#### **HPV Variant Testing**

To avoid persistence misclassification, all persons with type-specific high-risk HPV concordance at 0 and 12 months will have their specimens classified according to HPV-type variant. A variant analysis will be done by the Molecular Biology Laboratory, Centre of Translational Oncology, Instituto do Câncer do Estado de São Paulo, São Paulo, Brazil. 74, 75

# Methylation Testing

The second aliquot of each cryovial will be sent to Queen Mary University of London for host DNA and viral DNA methylation testing. The cryovial will be sent on wet ice and labeled only with the participant's unique ID.

# Pathology Readings

Biopsies specimens will be retained in the MCW Tissue Bank before forwarding to an MCW pathologist experienced in reading anal canal biopsies. The pathologist will use the most recent published criteria for describing the presence of dysplastic lesions.

Biopsies will be interpreted by a single experienced pathologist using a 2-tiered system (low-grade squamous intraepithelial lesion (LSIL) and high-grade squamous intraepithelial lesion (HSIL), and further classified by the applicable AIN subcategorization (anal intraepithelial neoplasia 1 (AIN1), AIN2 and AIN3). Low-grade AIN will be defined as the presence of AIN 1. High-grade AIN will be defined as the presence of AIN 2 or AIN 3. We plan to conduct p-16 staining on any histology samples that demonstrate a potential diagnosis for AIN 2/3. We anticipate 25% will need p-16 staining. The interpretation will drive clinical care and be available within 3 weeks of specimen collection. Biopsies will also be assessed for HPV genotypes.

#### EPIDEMIOLOGICAL AND STATISTICAL CONSIDERATIONS

#### Analysis

Participants will be randomized to either Arm 1 or Arm 2. For Aim 1 our primary analysis is to compare the proportion of those who comply with 0 and 12-month swabbing in the home- and clinic-based arms. Our primary endpoint, compliance, is categorized as "Yes" if a swab is returned at 0 and 12 months and "No" otherwise. The null hypothesis is that the proportion of those complying in each arm is the same. Under the intention-to-treat principle, all participants who are randomized are included in the analyses (primary and exploratory). We will compare the proportion of persons who are compliant in the two arms using a Mantel-Haenszel test for difference in proportions in a stratified design ( $\alpha$ =0.05). For sensitivity analysis we will also do a per protocol analysis comprised of compliant participants.

Participants will be considered non-compliant for either baseline or 12-month swab if they do not provide a swab within 30 days after kit mailing or clinic appointment. Persons randomized to arm 1 who "crossover" and attend a doctor's visit for anal cancer screening, including DNA collection, without returning a home-base kit, will be counted as non-compliant.

For Aim 2, to determine factors associated with compliance, we will use purposeful modeling strategies. We will perform a bivariate logistic regression for each factor, and those factors with a p-value less than 0.25 in the bivariate analysis will be included in a multivariable logistic regression model. Given that we expect 144 and 108 12-month swabs returned from arm 1 and arm 2, respectively, we can safely examine up to 10 factors simultaneously in the model and maintain the recommended minimum of 10 events per variable in the multivariable model. We will pay particular attention to the aforementioned HBM constructs, e.g., self-efficacy, to ascertain their ability to explain variance in compliance. Associations in the multivariable model will be considered significant with a p-value of <0.05. Adjusted and unadjusted odds ratios will be

reported with 95% CIs. We will regress compliance on covariates after adjusting for study arm, HIV status, race, and age (i.e., the randomization strata) and potential confounders identified with Directed Acyclic Graphs including insurance status, socioeconomic status and ethnicity.

For Aim 3, we will estimate the proportion who agree to HRA (with 95% confidence interval). After genotyping results are available, we will assess the proportion of persons agreeing and not agreeing to HRA who have high-risk persistence. Analysis of HRA CASI data will focus on HRA acceptability and use purposeful modeling strategies as with Aim 2 CASI analyses. Exploratory analysis of de-identified data may also be done by collaborators including the University of Chicago and Medical University of South Carolina.

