#### STUDY SYNOPSIS

A randomized, non-blinded study of compliance with annual home-based vs clinic-based DNA screening to detect anal canal precancers among 400 Milwaukee HIV+ and HIV- men who have sex with men (MSM) and transgender persons.

This is a prospective, randomized, two-arm clinical study to evaluate compliance with annual home-based vs clinic-based DNA screening of anal canal exfoliated cells among Milwaukee HIV+ and HIV- MSM and transpersons aged ≥25 years. At study entry, persons randomized to arm 1 will receive a home-based collection kit in the mail at 0 and 12 months and those in arm 2 will attend a clinic where a clinician will collect the exfoliated cell specimen at 0 and 12 months. Then, persons will receive HRA-directed biopsy to assess precancerous lesions by study arm. We hypothesize that a majority of persons will comply with annual screening with increased compliance among persons in the home-based arm vs clinic-based arm.

We will test our hypothesis with 3 specific aims:

- 1) Determine persons' compliance with annual anal HPV DNA specimen collection. The primary endpoint is compliance with swabbing at both baseline and 12 months.
- 2) Determine factors associated with annual screening compliance.
- 3) Establish the proportion of persons in each arm who agree to have HRA.

The current research will deliver:

- The first estimates of compliance with an annual biomarker screening program among MSM and transpersons;
- The first estimates of the relative ability of home-based screening to increase annual compliance;
- Evidence of the influence that home-based vs clinic-based screening has on the uptake of HRA-directed biopsy.

The proposed research could indicate that annual HPV DNA screening and subsequent HRA are acceptable to MSM and transpersons; thus, we will determine how high-risk persons are identified for HRA in light of limited HRA resources. The duration of each participant's activities is expected to be 12 months. The study is expected have participant activity from 2019 to 2023.

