In addition to a biomarker, a procedure like HRA with directed biopsy is needed to identify precancerous lesions or cancer in the anal canal; however, some persons may refuse to undergo the invasive procedure of HRA with biopsy. The studies are equivocal with regard to HRA acceptability among MSM with one finding significant pain and bleeding with HRA, and a second finding little. The current study will assess a real-world scenario where a certain proportion of persons, even though potentially compliant with annual screening, may decide to forgo HRA.

We are keenly aware that introduction of the more invasive HRA may also influence those who choose to consent and those who are compliant with repeated sampling; thus, we will collect reasons for declining consent and data on those lost to follow up.

Our proposed experimental design in Aim 1 and 2, plus our prior work in HPV natural history and anal cancer screening positions us to identify 12-month persistence among persons and make important observations about which of these HPV-persistent persons complied with HRA.  With this design we can efficiently test important questions: Will MSM and transpersons comply with annual biomarker screening? Will home-based sampling increase compliance? What other factors are associated with repeated annual screening? What proportion of persons will agree to clinic-based HRA-directed biopsy (the definitive test for precancerous lesions) after home-based self-sampling? What HPV DNA biomarkers efficiently detect anal high-grade lesions? Answers to these questions support our long-term goal of reducing morbidity and mortality from anal cancer given an increasing incidence of disease and very limited impact of HPV vaccination on adults given very low uptake to date.

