#### Inclusion Criteria

- Be  $\geq$  25 years of age
- Sex at birth is male or gender identity is a transgender person
- Acknowledge sex with men in the last 5 years, or identify as gay or bisexual
- Understand and be willing to give informed consent
- Be willing to be randomized and able to comply with the protocol
- Spanish and/or English speakers/readers, and
- HIV+ or HIV-

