#### PARTICIPANT ACTIVITIES

## **Self-Swabbing Kits**

After completing the CASI baseline survey, participants will get information about receiving a swabbing kit in the mail or making a clinic appointment. Participants in arm 1 will be sent a kit within 2 weeks while those in arm 2 will be asked to attend a clinic appointment in the next 2 weeks. Persons in arm 2 will be provided with names and contact information for a participating clinic and asked to call that clinic to set up an appointment. If they have not made an appointment within 48 business hours, they will be contacted up to three times and asked to make the appointment. Clinic or study staff (depending on clinic) will then contact participants within 24 business hours if the participant does not show for an appointment. Clinic staff will attempt to contact participants 3 times over one month before being classified as non-compliant for Visit 1.

A mock-up of the arm 1 self-swabbing kit will be pre-tested with the CAB. The kit box will not be identifiable as having health-related contents. Shipments will be logged, and the arm 1 participant will be notified upon shipment. Participants not confirming kit receipt within 7 days will be prompted about the kit receipt. The kit will include return packaging, instructions for returning the sample, self-sampling instructions, a biohazard bag, a swab, and a vial of 2 mL of standard transport media (STM) pre-labeled with a participant unique ID, and kit # (i.e., kit 1 or 2). STM is classified as a non-hazardous substance. To assess specimen exposure to extreme temperatures during mail transit, the kit will be packaged within insulation (e.g., Styrofoam) and include a temperature-monitoring device (LogTag Recorders, Auckland, New Zealand).

Home-based participants' kits will include instructions for self-swabbing written at a 6th-grade reading level in either English or Spanish. The instructions will be modeled after already-tested self-sampling instructions and presented to the CAB.

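### The Aim 1 per-protocol sensitivity analysis selects participants on the primary endpoint itself, so it compares 100% with 100% and cannot test robustness

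*Combined protocol and SAP*

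**What the plan says.** The Study Synopsis of the combined protocol and SAP states: "The primary endpoint is compliance with swabbing at both baseline and 12 months". The Analysis section scores a participant Yes "if a swab is returned at 0 and 12 months" and No otherwise. It adds a timing rule: a participant is non-compliant for either round "if they do not provide a swab within 30 days after kit mailing or clinic appointment". It also has a crossover rule, under which an arm 1 participant who is screened by a doctor but sends back no kit counts as non-compliant.

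The primary comparison is by intention to treat in all randomised participants, with a Mantel-Haenszel test at alpha 0.05. The plan then says: "For sensitivity analysis we will also do a per protocol analysis comprised of compliant participants". No other sensitivity analysis is named for Aim 1, and the per-protocol set is not defined further anywhere.

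Related words are used in other senses elsewhere. The Self-Swabbing Kits section describes contact attempts with clinic-arm participants "before being classified as non-compliant for Visit 1", which concerns a single visit. The Background speaks of "which of these HPV-persistent persons complied with HRA", and the Inclusion Criteria require a person to "Be willing to be randomized and able to comply with the protocol".

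**The concern.** A per-protocol analysis normally keeps people who received the assigned intervention as planned and then compares an outcome among them. Here adherence is the outcome. A set made up of compliant participants contains only endpoint successes, so nothing is left to compare between arms.

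What is at stake is the one planned check on the Aim 1 result. Followed literally, it yields nothing. If the set is instead settled at analysis time, its definition is chosen after the fact in a trial that is not blinded to study staff. Either way, a reader of the final report could be told that a per-protocol analysis supported the primary finding when it could not have contradicted it.

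**Working it through.** **Inputs (Sample Size Estimation).** About 200 per arm; 10% loss to follow-up; home return 80% at baseline and 80% of those followed at 12 months; clinic return 70% and 60%.

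**The plan's own figures.**
- Home: 200 × 0.90 = 180; 180 × 0.80 = 144; 144/200 = 72%.
- Clinic: 180 × 0.60 = 108; 108/200 = 54%.
- Difference: 0.72 − 0.54 = 0.18. These agree with the plan.

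The counts 144 and 108 are derived as 12-month returns but are used as compliance. Treating them as both-swab compliers is an assumption.

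**Literal reading: the set is endpoint = Yes.**
- Kept: 144 home and 108 clinic, 252 of 400 (63%). Dropped: 56 home and 92 clinic, 148 in all, who are exactly the non-compliers.
- Proportions: 144/144 and 108/108, difference 0.
- Mantel-Haenszel, with n1 = 144, n2 = 108, N = 252, m1 = 252 compliers and m0 = 0 non-compliers:
  - observed minus expected = 144 − 144 × 252/252 = 0;
  - variance = n1 × n2 × m1 × m0 / (N² × (N − 1)) = 144 × 108 × 252 × 0 / (252² × 251) = 0;
  - the statistic is 0/0.
- Every stratum of a stratified version also has m0 = 0, so stratifying changes nothing.
- The result does not depend on the counts. Any numbers of compliers, including equal or reversed proportions by arm, give 100% against 100%.
- The 30-day rule does not help. Anyone who meets it in both rounds has returned both swabs and is an endpoint Yes.

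**Alternative reading: the set is baseline-swab compliers.**
- Kept: 200 × 0.80 = 160 home and 200 × 0.70 = 140 clinic. Dropped: 40 and 60.
- If every 12-month returner also returned at baseline: 144/160 = 90.0% and 108/140 = 77.1%, a difference of 12.9 points. By intention to treat it is 18.0.
- The documents do not give the overlap of the two rounds, and the section on the 12-month swab says that people lost to follow-up are still approached for it. The planned margins alone allow 160 + 144 − 200 = 104 to 144 both-swab returners at home (65.0% to 90.0% of 160). In the clinic arm they allow 140 + 108 − 200 = 48 to 108 (34.3% to 77.1% of 140). The 12.9 points is therefore an illustration, not a forecast.
- Whatever the overlap, this analysis asks about 12-month return among those who started, in two groups that the plan expects to be selected at different rates.

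**The case against.** The strongest case against is that little depends on this sentence. The primary analysis keeps all randomised participants, and no decision, alpha or sample size rests on the per-protocol result. Run literally, it fails visibly and cannot produce a misleading estimate. That stands, and it limits the seriousness of the point.

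Second, the sentence names no outcome. Restricting to both-swab compliers would not be degenerate for Aim 3, the uptake of high-resolution anoscopy. That also stands, so the point is confined to Aim 1. But the sentence sits in the Aim 1 paragraph and directly follows the Aim 1 test.

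Third, the authors may have meant adherence to assigned procedures, since the documents use comply more broadly elsewhere. This is plausible as intent, but no such set is defined. The crossover rule does not define one either: it makes those participants endpoint failures and excludes nobody.

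A reader might go further and infer that the compliance window itself is unworkable. It runs from kit mailing in one arm and from the clinic appointment in the other, so a clinic participant who never books has no start date. The documents do not support that. A person who never books gives no clinic swab and is already No. The Self-Swabbing Kits section also covers this person: "If they have not made an appointment within 48 business hours, they will be contacted up to three times". Nor does the defect call for one clock from randomisation. A limit of 14 + 30 = 44 days, for example, matches only a kit mailed on day 14; a kit mailed on day 1 now has a limit of day 31. A swab at a later-booked clinic appointment counts now but could fail at 44 days. Such a rule could reclassify people in both directions.

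**Conclusion.** The point holds for the Aim 1 comparison. As written, the per-protocol analysis is 100% against 100% by construction and carries no information about the effect of home-based sampling. This needs no assumption beyond the plan's own definition of compliance; the counts 144 and 108 only illustrate it. Under the baseline-only reading the analysis can be computed, but it is selected after randomisation on part of the endpoint. Its 12.9 points, against 18.0 by intention to treat, rests on assuming that all 12-month returners also returned at baseline.

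Two stronger conclusions should not be drawn. A reader might infer that the primary result is compromised; it is not, because the intention-to-treat analysis does not use this set. A reader might also multiply the two return rates as if they were independent, giving 0.80 × 0.72 = 57.6% and 0.70 × 0.54 = 37.8%. The plan states 72% and 54% as its compliance figures and gives no basis for independence.

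This should be fixed in the SAP; it is not a design fault.

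**What to change.** - Delete the per-protocol analysis of compliant participants for Aim 1. Otherwise, define its set without reference to swab return, for example by excluding only participants found to have been ineligible at randomisation, judged without sight of swab status.
- Name one sensitivity analysis that keeps all randomised participants. Count as compliant anyone whose arm-assigned swab was received for both the 0- and 12-month rounds, regardless of the 30-day limit. In arm 1 only the home-kit swab counts, not the clinician swab taken at the baseline clinic visit. This follows the principle of the existing crossover rule.

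The cost is SAP wording, one extra tabulation and a check that clinic swab dates are recorded. Kit shipment and receipt are logged, but the documents do not state a logged date for clinic swabs. Late swabs may be few, because contact attempts run for about a month and the documents do not say whether later swabs are accepted. The result may therefore lie close to the intention-to-treat result. An eligibility-based set may likewise exclude few people or none.

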After receipt of the kit, participants will be instructed to wash hands with soap and water. The instructions will ask the participant to get into a comfortable position (e.g., one foot on a toilet), hold the swab in their dominant hand, pull back a buttock with the other hand and then insert the swab gently into the anal canal about 2-3 inches. The participant will then twirl the swab, count slowly to 10, and remove the swab, all the while applying swab pressure to the anal canal walls. After collecting the specimen, persons will place the swab into the tube, and then place the tube into the biohazard bag.  Kit instructions will ask participants to record the date of the swabbing. Participants will be asked to wait until 24 hours after last receptive anal sex before self-swabbing.

Participants will be asked to return the kit within 3 days by overnight mail to the MCW Tissue Bank. The receipt date will be logged at the MCW Tissue Bank. When MCW receives the kit, the participant will be sent a link to complete the post swab 1 CASI online. Study staff will contact participants who have not returned kits within 2 weeks of kit delivery. Study staff will attempt to contact participants 3 times over one month after kit delivery before recording them as non-compliant.

All persons in the home-based arm 1 will be asked to attend a study clinic of their choice to receive height, weight, and waist circumference measurements, a clinician swab and a DARE to rule out prevalent anal cancer. If there is a finding on DARE, then standard clinical practices will be followed.

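### The 30-day limit in the primary endpoint runs from kit mailing in arm 1 but from the appointment itself in arm 2, and other non-compliance rules are left unreconciled

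*Combined protocol and SAP*

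**What the plan says.** The Analysis section makes compliance the primary endpoint. A participant is compliant "if a swab is returned at 0 and 12 months" and otherwise not. It then gives a time limit for each swab: a person fails "if they do not provide a swab within 30 days after kit mailing or clinic appointment".

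The Self-Swabbing Kits section, under Participant Activities, sets out how each clock comes to start.

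- **Arm 1.** "Participants in arm 1 will be sent a kit within 2 weeks". Shipment is logged, and on return "The receipt date will be logged at the MCW Tissue Bank". The section then has its own rule: "Study staff will attempt to contact participants 3 times over one month after kit delivery before recording them as non-compliant".
- **Arm 2.** The participant is given a clinic's details and "asked to call that clinic to set up an appointment". Those who delay are then chased by staff: "If they have not made an appointment within 48 business hours, they will be contacted up to three times". After a sentence on no-shows comes another rule: "Clinic staff will attempt to contact participants 3 times over one month before being classified as non-compliant for Visit 1". The start of that month is not given.

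The Clinic-Based Swabbing section has the clinician take the swab at the appointment and asks participants to come in the first two weeks after randomisation. The section on swabbing at 12 months says that procedures repeat those at baseline, with up to four reminders. No section says which of the three non-compliance rules decides the endpoint.

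**The concern.** Two separate problems affect how the primary endpoint is scored.

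First, the time limit does different work in the two arms. In arm 1 the 30 days must cover outbound post, self-swabbing and return. In arm 2 the starting event and the outcome are the same visit, so nobody swabbed at a first appointment can exceed the limit, however late that appointment falls. An outcome rule that works differently by arm is a measurement difference, and neither randomisation nor intention-to-treat analysis removes it. The plan takes this kind of risk seriously elsewhere: under Results Given to Participants, the arm 1 rectal examination is delayed so that it does not influence swab 1 compliance.

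Second, the same word, non-compliant, is attached to different clocks. Two analysts following different sections could score the same arm 1 participant differently. Compliance is also the dependent variable in Aim 2, so any ambiguity carries over to that analysis.

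**Working it through.** **Inputs.** Day 0 is randomisation. Let m be the day the kit is mailed (up to 14, Self-Swabbing Kits), t the days of outbound post (not given), r the day the kit is returned, and a the day the first appointment is attended (requested by day 14, not enforced). One month is taken as 30 days. The plan states no figure of its own on this point to reproduce.

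**Step 1: the scoring rules.**

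- Arm 1, Analysis section: compliant if r − m ≤ 30.
- Arm 1, Self-Swabbing Kits section: inside the month if r − (m + t) ≤ 30.
- Arm 2, Analysis section, first appointment attended: a − a = 0 ≤ 30, so compliant for every a.

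**Step 2: both two-week targets just met.** Arm 1: 14 + 30 = day 44. Arm 2: 14 + 30 = day 44. The deadlines then coincide, so the asymmetry comes from what happens when a target is missed or a visit is late.

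**Step 3: three cases.** The last column is a common-origin window using the plan's own 14 + 30 days.

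| Case | Analysis rule | One month from delivery | 44 days from randomisation |
|---|---|---|---|
| Arm 1: mailed day 0, delivered day 3, returned day 32 | 32 − 0 = 32, fails | 32 − 3 = 29, inside | 32, counts |
| Arm 1: mailed day 14, returned day 50 | 50 − 14 = 36, fails | 36 − t, inside only if t ≥ 6 | 50, fails |
| Arm 2: first appointment attended day 50 | 50 − 50 = 0, counts | not applicable | 50, fails |

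Row 1 shows the conflict between sections. The days on which the two arm 1 rules disagree run from m + 30 to m + t + 30, so the width of the conflict is the outbound post time. Rows 2 and 3 show the difference by arm under the Analysis rule.

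**Step 4: could the arm 2 one-month rule cap late attendance?** If it governed and its month began on day s, a day-50 visit would be too late when s + 30 < 50, that is s < 20. With no stated start, this cannot be settled.

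**Step 5: scale only, not an estimate.** Assume 200 per arm, equal true compliance in both arms between 54% and 72% (the plan's two planning values), and one arm under-counted by d. With a pooled two-sided test at 5% (unstratified), P(reject) = Φ((d − 1.96·se0)/se1) + Φ((−d − 1.96·se0)/se1), where se0 and se1 are the pooled and unpooled standard errors. For 54% and d = 0.03, se0 and se1 are both about 0.0499, so P = Φ(−1.36) + Φ(−2.56) = 0.092. Over the 54% to 72% range, P is 6.9–7.2% for d = 2 points, 9.2–10.1% for 3 points and 17.0–19.2% for 5 points. The documents give no time-to-swab or time-to-appointment data from which to choose d.

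**The case against.** The best reply is that the plan has one endpoint rule and two follow-up procedures. The Analysis section defines the endpoint and states its limit for both arms and both time points. The one-month sentences sit under Participant Activities and describe how long staff keep contacting people. One month and 30 days are almost the same length, so the arm 1 conflict is little more than outbound post. Arm 2 attendance is requested within two weeks and chased by telephone, which should make very late first visits uncommon.

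Most of this stands. It is the natural reading, and the calls do limit late booking. But the calls set no deadline, the three rules share one term, and no sentence gives precedence. The point that the arm 2 limit cannot fail a late first visit does not depend on the operational sections.

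A reader might go further in three ways that the documents do not support.

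- **That one arm is given a definite number of extra days.** Deadlines depend on individual mailing and booking dates. Setting one participant's extreme against another's, or a different rule for each arm, does not give a between-arm difference. With both targets just met, the deadlines are the same.
- **That the rule is biased against home sampling.** That would need evidence that late first visits occur and are more often counted than late kits are excluded. No such data are given.
- **That people who never book are left unscored.** They are non-compliant by the residual clause of the endpoint definition. The gap concerns only those who book late, miss an appointment or rebook.

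**Conclusion.** The concern holds for the endpoint definition and should be fixed. Under the Analysis rule, the 30-day limit can exclude a late arm 1 return but not a late first appointment in arm 2. The mailing origin in that section also conflicts with the delivery origin in the Self-Swabbing Kits section for arm 1. Both follow from the text, and each is shown by a case in which the score turns on the clock used.

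The size and direction of any effect on the compliance difference cannot be derived. The worked cases assume that a month is 30 days and that the return day is the day the swab counts as provided. The day-50 comparison applies only under the Analysis rule. It could change if the delivery rule governed and outbound post took at least 6 days, or if the undated arm 2 month governed and began before day 20.

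**What to change.** 1. State that the rule in the Analysis section decides the endpoint at both time points, and that the one-month rules in the Self-Swabbing Kits section are contact procedures only.
2. In the Analysis section, say whether the first or a rescheduled appointment starts the arm 2 clock, and how a person who has not booked, or who books late, is scored.
3. Prespecify a sensitivity analysis with the same origin and number of days in both arms: for example 44 days from randomisation for swab 1, and an equal window around a common 12-month due date for swab 2. Use the logged receipt date in arm 1 and the visit date in arm 2.
4. Add a second sensitivity analysis that counts arm 1 from delivery, where delivery dates are known.

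Date the change before any comparison by arm. The trial is unblinded, version 4.5 was approved in July 2023, participant activity was expected to run to 2023, and the team reviews swab completion weekly (the protocol does not say whether by arm).

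The cost is a short amendment and some extra analysis. The common-origin analysis needs randomisation, receipt and visit dates. Delivery dates may be incomplete, because the kit procedure describes only participant confirmation, with a prompt after 7 days. No section says that appointment dates are logged, and item 2 needs them.

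Two cautions apply. A randomisation origin puts mailing delay and post inside the arm 1 window only, so it suits a sensitivity analysis better than a replacement for the primary rule. The swab 2 window should also keep the interval between swabs close to 12 months. A window opening at the 11.5-month reminder (11.5 × 365.25/12 ≈ day 350) would admit a pair only 350 − 44 = 306 days apart.
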